**Document History – Changes compared to previous final version of SAP**

---

[figure not shown]
Date	Time point	Reason for update	Outcome for update	Section and title impacted (Current)
30-Jul-2021	Prior to DB lock	Creation of final version	N/A - First version	NA

---

---

[figure not shown]

**List of abbreviations**

AAV	Adeno-associated virus
AE	Adverse Event
AESI	Adverse Event of special interest
ALP	Alkaline phosphatase
ALT	Alanine aminotransferase
AST	Aspartate aminotransferase
AT	Aminotransferase
BiPAP	Bilevel Positive Airway Pressure
BSID	Bayley Scales of Infant and Toddler Development
BUN	Blood urea nitrogen
cDNA	complimentary deoxyribonucleic acid
CHOP-INTEND	Children's Hospital of Philadelphia Infant Test of Neuromuscular Disorders
CK	Creatine kinase
CK-MB	Creatinine kinase-muscle/brain
cm	Centimeter
COVID	Corona virus disease
CRF	Case Report Form
CSR	Clinical Study Report
CTCAE	Common Terminology Criteria for Adverse Events
DILI	Drug-induced liver injury
dl	deciliter
DMS	Document Management System
ECG	Electrocardiogram
eCRF	Electronic case report form
ELISA	Enzyme-linked immunosorbent assay
ELISpot	Enzyme-linked ImmunoSpot
FAS	Full Analysis Set
FDA	Food & Drug Administration
g	Gram
GGT	Gamma glutamyl transferase
HEENT	Head, eyes, ears, nose, throat
hSMN	Hereditary sensory motor neuropathy
IA	Interim Analyses
ICH	International Conference on Harmonization
ITT	Intent-to-Treat
IV	intravenous
Kg	kilogram
Lbs	Pounds
LFE	Liver function enzyme
MCH	Mean corpuscular hemoglobin
MCHC	Mean corpuscular hemoglobin concentration
MCV	Mean corpuscular volume
MedDRA	Medical Dictionary for Drug Regulatory Affairs
MGRS	Multicenter Growth Reference Study
mRNA	Messenger ribonucleic acid
PBMC	Peripheral blood mononuclear cell

PCS	Potentially clinically significant
PK	Pharmacokinetics
PPS	Per-Protocol Set
PRO	Patient-reported Outcomes
QTcB	Corrected Q-T interval using Bazett's formula
QTcF	Corrected Q-T interval using Fridericia's formula
RAP	Reporting & Analysis Process
RBC	Red blood cell
RDW	Red cell distribution width
SAE	Serious Adverse Event
SAP	Statistical Analysis Plan
SAS	Statistical Analysis System
SD	Standard deviation
SFC	Surface
SMA	Spinal muscular atrophy
SMN	Survival motor neuron
SOP	Standard operating procedure
TBL	Total bilirubin
TEAE	Treatment-emergent Adverse Event
TFLs	Tables, Figures, Listings
ULN	Upper limit of normal
USB	Universal serial bus
Vg	Vector genome
VH	Very high
VL	Very low
WBC	White blood cell
WHO	World Health Organization

---

[figure not shown]
## 1 Introduction

The purpose of this document is to provide further details about the statistical analysis methods, data derivations and data summaries to be employed in the study protocol COAV101A12304 (AVXS-101-CL-306): *Phase 3, Open-Label, Single-Arm, Single-Dose Gene Replacement Therapy Clinical Trial for Patients with Spinal Muscular Atrophy Type 1 with One or Two SMN2 Copies Delivering OAV101 by Intravenous Infusion*. This statistical analysis plan (SAP) has been based on International Conference on Harmonization (ICH) E3 and E9 guidelines and in reference to protocol version 6.0, dated 11 Nov 2020. The SAP describes the implementation of the statistical analysis for clinical study reporting planned in the protocol. It covers statistical analysis, tabulations and listings of all data including effectiveness and safety data.

### 1.1 Study design

This is a Phase 3, open-label, single-arm, single-dose trial of OAV101 (gene replacement therapy) in patients with SMA Type 1 with one or 2 copies of SMN2. At least 6 patients < 6 months (< 180 days) of age at the time of gene replacement therapy (Day 1) were planned to be enrolled as part of a combined analysis with Study COAV101A12303. But at the time of this protocol was amended (Protocol version 6.0 amendment 5 dated 11 Nov 2020), the enrollment was closed with 2 active enrolled patients. The combined analysis is no longer to be performed.

The trial includes 3 trial periods: screening, gene replacement therapy, and follow-up (Figure ). During the screening period (Days -30 to -2), patients whose parent(s)/legal guardian(s) provide informed consent will undergo screening procedures to determine eligibility for trial enrollment. Patients who meet the entry criteria will enter the in-patient gene replacement therapy period (Day -1 to Day 3). On Day -1, patients will be admitted to the hospital for pre-treatment baseline procedures. On Day 1, patients will receive a one-time intravenous (IV) infusion of the equivalent of OAV101 cohort 2 dose received in the AVXS-101-CL-101 trial over approximately 60 minutes and will undergo in-patient safety monitoring over the next 48 hours. Patients may be discharged 48 hours after gene replacement therapy, based on Investigator judgment. During the outpatient follow-up period (Days 4 to End of Trial at 18 months of age), patients will return at regularly scheduled intervals for efficacy and safety assessments until the patient reaches 18 months of age. Any missed visit should be rescheduled as soon as possible, but within the visit windows shown in the Schedule of Assessments. All visits will be scheduled based on a 30-day month calendar.

**Figure 1 - Trial Design**

Note: After the End of Trial visit at 18 months of age or at the time of early discontinuation patients will be invited to participate in a long- term follow-up study conducted under a separate protocol.

a All post-treatment visits will be relative to the date on which gene replacement therapy is administered until the patient is 14 months of age, after which all visits will be relative to the patient's date of birth. *Note: Depending on the patient's age at dosing, the duration of participation at the end-of-trial visit can vary from approximately 12 months (baby dosed at approximately 6 months of age) to approximately 18 months (baby dosed near birth "0 months of age").* All visits will be scheduled based on a 30-day month calendar.

After dosing follow-up visits will be conducted according to the Schedule of Assessments. All post-treatment visits will be relative to the date on which gene replacement therapy is administered until the patient is 14 months of age, after which all visits will be relative to the patient's date of birth. For the 14 and 18 months of age visits, the patient will return within 0 to 14 days after the date on which the patient reaches 14 and 18 months of age, respectively. The 18 months of age visit will also serve as the End of Trial visit. After the End of Trial visit, patients will be invited to participate in a long-term follow-up study under a separate protocol. Patients who discontinue prematurely will also be invited to participate in the long-term follow-up study.

In an attempt to dampen the host immune response to the AAV-derived therapy, all patients will receive prophylactic prednisolone.

In the event that unforeseen catastrophic or other serious situations (such as the COVID-19 pandemic) impact the ability to conduct the study on-site, alternative methods of continuing study assessments may be implemented. Alternative visits include phone calls, virtual contacts through teleconsult or videoconference, or visits by site staff/home nursing providers to the

patient's home depending on local regulations, institutional policies, and capabilities of the investigative site. Alternative visits may take place instead of on-site visits until such time that the patient can safely return to the site.

Throughout the study, the scheduling of study visits should adhere to the overall study schedule and visit windows defined in the protocol. For each study visit, all study procedures and assessments should be performed or completed in accordance with the schedule of events. Local institutions or other alternatives may be utilized.

Importantly, in instances in which the final scheduled study visit is not possible to be conducted at the study site, the final scheduled study visit should be performed all or by an alternative visit within the protocol-defined visit window. Critical data that pertain to the primary and secondary endpoints and other information such as adverse events, concomitant medications, use of feeding or ventilatory support, or other safety data that may be obtained remotely should be collected as part of the final study visit and within the protocol-defined visit window.

Procedures such as laboratory and other safety assessments that cannot be performed or obtained as part of a remote visit may be performed separately and preferably within the protocol-defined visit window.

## 1.2 Study objectives, endpoints and estimands

This trial will assess the efficacy of OAV101 administered IV in terms of functional independent sitting and survival rate in symptomatic SMA Type 1 patients who are homozygous negative for SMN1 exon 7 and have 2 copies of SMN2 without the SMN2 genetic modifier. Only objectives and endpoints in the protocol are listed below.

**Table 1 Objectives and related endpoints**

Objective(s)	Endpoint(s)
Primary objective(s)	Endpoint(s) for primary objective(s)

• EFFICACY: Determine efficacy by demonstrating achievement of developmental milestone of sitting without support up to 18 months of age as assessed by WHO Motor Developmental Milestones

	

• Achievement of the ability to sit without support for at least 10 seconds at any visit up to and including the 18 months of age visit. It is defined by the WHO MGRS, confirmed by video recording, [REDACTED]

Secondary objective(s)	Endpoint(s) for secondary objective(s)

• Determine efficacy based on survival at 14 months of age. Survival is defined by the avoidance of combined endpoint of either (a)

	

• Survival at 14 months of age amongst symptomatic SMA Type 1 patients who are homozygous negative for SMN1

Objective(s)	Endpoint(s)

death or (b) permanent ventilation which is defined by tracheostomy or by the requirement of <math>\geq 16</math> hours of respiratory assistance per day (via non-invasive ventilatory support) for <math>\geq 14</math> consecutive days in the absence of an acute reversible illness, excluding perioperative ventilation. Permanent ventilation, so defined, is considered a surrogate for death.
 

• SAFETY: To evaluate the safety and tolerability of OAV101-IV in patients with SMA Type 1

	
exon 7 and have 2 copies of SMN2 without the SMN2 genetic modifier (see further detail followed the table)
 

• Incidence of treatment emergent adverse events (TEAEs) and serious TEAEs (SAEs)

• Evaluation of changes from baseline in vital signs, and clinical laboratory results

Exploratory objective(s)	Endpoint(s) for exploratory objective(s)

### **1.2.1 Primary estimand(s)**

Not applicable

### **1.2.2 Secondary estimand(s)**

Not applicable

## **2 Statistical methods**

### **2.1 Data analysis general information**

Novartis Gene Therapies, Inc. will be performing final analysis.

Analyses will be performed using [REDACTED]

There are no interim analyses. The final analysis will be composed by individual data listings and patient profiles after the final database lock. No data aggregations, summary tables or inferential statistical approaches will be performed.

---

### 2.1.1 General definitions

“Day 1” is defined as the day of gene transfer, “Day -1” the day before. Gene transfer is the single-time study treatment as gene therapy infusion. The dose is the total vector genome (vg) delivered, the human SMN cDNA sequence, corresponding to the mature mRNA, cloned into the self-complementary AAV vector plasmid, given in vg per subject weight in kilogram (kg) on Day -1.

For any event, “study day” is defined as the time from Day 1 to the day of the event in days plus 1 day.

“Baseline” refers to a non-missing measurement or evaluation made prior to initiation of gene therapy infusion. If there are multiple measurements prior to the initiation of gene therapy infusion, only the latest measurement will be considered as baseline for analysis purposes. If these multiple measurements occur at the same time or time is not available, then the average of these measurements (for continuous data) or the worst among these measurements (for categorical data) will be considered as the baseline value. This same baseline value will be used for the treatment and post-treatment periods.

“Last contact” refers to the last study visit. If not terminated early, it is the end-of-trial visit at 18 months of age. “Age” will be expressed in months and rounded to one decimal place, where age in months is the time from birth to a date in days, plus 1 day, divided by 30. The final value for each patient is the first non-missing value on or after the participant reaches 18 months of age (540 days) with an upper limit of 570 days. Thus, the earliest visit between 540 and 570 days of age, inclusive, will be used in the “18 months of age” analysis.

Analysis visits are defined per month following a visit windowing approach in two different schedules, one based on study day post dosing and another one based on patient age. For by-visit efficacy endpoints, the time windows describe how efficacy data will be assigned to protocol-specified time points. For a Month K,  $K > 1$ , the time windows are around Study Day  $K*30$ , the nominal time, in a range of -15 to +14 days. Month 1 spans from Study Day 1 to 44. If more than one efficacy observation for a specific assessment is included in a time window, the assessment closer to the nominal time will be used. If there are two efficacy observations

equally distant to the nominal time, the latest one will be used in analyses. Visits at 14 and 18 Months of Age follow an analysis window of 420 to 434 and 540 to 554 days of age, respectively. CHOP-INTEND scores and Bayley Scales will also be presented by analysis visit following an age based visit windowing approach for M months of age in the range of  $M*30$  to  $(M+1)*30-1$  days since birth.

“Bilevel Positive Airway Pressure” (BiPAP) is a form of non-invasive mechanical pressure support ventilation.

---

“Permanent ventilation” is defined as a requirement of  $\geq 16$ -hour respiratory assistance per day (includes BiPAP) continuously for  $\geq 14$  days in the absence of an acute reversible illness, excluding perioperative ventilation.

A “responder” is a patient who demonstrates achievement of an endpoint at any post-procedure visit up to and including the 18-months-of-age visit.

An “Adverse Event” (AE) is any untoward medical occurrence in a clinical investigation subject, which does not necessarily have a causal relationship with the drug or device under study.

A “treatment-emergent Adverse Event” (TEAE) is any AE whose onset or worsening occurred on or post Day 1.

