4. LIST OF ABBREVIATIONS AND DEFINITIONS OF TERMS

The following abbreviations and specialist terms are used in this trial protocol.

Abbreviation or Specialist Term	Explanation
AAV	Adeno-associated virus
AAV9	Adeno-associated virus serotype 9
ADL	Activities of daily living
AE	Adverse event
AESI	Adverse events of special interest
ALP	Alkaline phosphatase
ALT	Alanine aminotransferase
APTT	Activated partial thromboplastin time
ASO	Antisense oligonucleotide
AST	Aspartate aminotransferase
AT	Aminotransferase
BSIDv03	Bayley Scales of Infant and Toddler Development, version 3
BUN	Blood urea nitrogen
CB	Chicken- β -actin-hybrid
cDNA	complimentary Deoxyribonucleic Acid
cGMP	Current Good Manufacturing Practice
CHOP INTEND	Children's Hospital of Philadelphia Infant Test of Neuromuscular Disorders
CK	Creatine kinase
CMV	Cytomegalovirus
CNS	Central nervous system
CTCAE	Common Terminology Criteria for Adverse Events
Day 1	First 24-hour interval after the start of gene replacement therapy infusion
Day -1	24-hour interval prior to the start of gene replacement therapy infusion
DMC	Data Monitoring Committee
DRG	Dorsal root ganglia
DSMB	Data Safety Monitoring Board
ECG	Electrocardiogram
eCRF	Electronic Case Report Form
ELISA	Enzyme-linked immunosorbent assay
ELISpot	Enzyme-linked immunospot
ET	Early termination
FVB	Friend Virus B-Type
GCP	Good Clinical Practice
GFP	Green fluorescent protein
GGT	Gamma glutamyl transferase
GLP	Good Laboratory Practice
HEENT	Head, eyes, ears, nose, and throat

Abbreviation or Specialist Term	Explanation
HgB	Hemoglobin
HIV	Human immunodeficiency virus
ICD-10 code	International Statistical Classification of Diseases and Related Health Problems
ICF	Informed consent form
ICH	International Council for Harmonisation
IEC	Independent Ethics Committee
IFN- γ	Interferon gamma
INR	International normalized ratio
IRB	Institutional Review Board
ISF	Investigator site file
IT	Intrathecal
ITR	Inverted terminal repeat
ITT	Intent-to-treat
IV	Intravenous
LFE	Liver function enzymes
LFT	Liver function test
LV EF	Left ventricular ejection fraction
LV FS	Left ventricular fractional shortening
MAP	Managed Access Program
MedDRA	Medical Dictionary for Regulatory Activities
MGRS	Multicenter Growth Reference Study
NCI	National Cancer Institute
NHP	Non-human primates
NOAEL	No observable adverse effect level
PBMC	Peripheral blood mononuclear cells
PICU	Pediatric intensive care unit
PNCR	Pediatric Neuromuscular Clinical Research Network
RNA	Ribonucleic acid

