12.1.2. Physical Examinations

Physical examinations will be conducted by the Investigator or designee as specified in the SoA ([Appendix 1](#)). The Day 1 physical examination will be performed prior to the start of gene replacement therapy infusion. Physical examinations include a review of the following systems: head, eyes, ears, nose and throat (HEENT), lungs/thorax, cardiovascular, abdomen, musculoskeletal, dermatologic, lymphatic, neurologic, and genitourinary. Specifically, the neurological exam should include detailed, age-appropriate sensory testing (such as examination of proprioceptive, vibratory, tactile and pain sensation) at each visit. Any clinically significant abnormal finding should be recorded as an adverse event. Further clinical evaluation should be considered as per judgment of the investigator.

The head circumference shall be measured with each physical examination. To measure head circumference, the examiner should securely wrap a flexible measuring tape around the circumference of the head, above the eyebrows over the broadest part of the forehead, above the ears, and over the most prominent part of the occiput. The measurement should be taken 3 times, and the largest measurement should be recorded to an accuracy of 0.1 centimeters.

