13.3. Recording Adverse Events

Adverse events spontaneously reported by the patient and/or in response to an open question from the trial personnel or revealed by observation will be recorded during the trial at the investigational site. Information about AEs (related and unrelated) after signing of the informed consent form until the last study visit are to be collected. Serious adverse event information will be collected from signing of the informed consent form through 30 days after the last trial visit. The AE term should be reported in standard medical terminology when possible. For each AE, the Investigator will evaluate and report the onset (date and time [if start date during inpatient period]), resolution (date and time [if start date during inpatient period]), intensity, causality, action taken, serious outcome (if applicable), and whether or not it caused the patient to discontinue the trial.

It is important to distinguish between serious and severe AEs. Severity is a measure of intensity whereas seriousness is defined by the criteria under [Section 13.1.2](#). An AE of severe intensity may not be considered serious.

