22. APPENDICES**APPENDIX 1. SCHEDULE OF ASSESSMENTS**

Trial Period	Screening	Gene Replacement Therapy (In-patient)					Follow-up (Outpatient)										Notes
		-30 to -2	-1	1	2	3	7	14	21	30	44	60 (or Month 2)	72	90 (or Month 3)	Month 4,5,7,8,10,11,13	Month 6,9,12	
Nominal Study Day (Visit Relative To Dose)																	
Visit According To Months of Age															14,16,17	15	
Window	(No Window)					± 2 days				± 7 days (Except +0–14 days at 14 Months of Age)				+0–14 days			
Informed Consent	X																See Section 18.3
AVXS-101 Infusion			X														See Section 10.6. Day 1 assessments will be performed prior to the start of gene replacement therapy infusion.
BSIDv03/WHO Developmental Milestones (with video)	X							X		X		X		X		X	See Sections 11.1, 11.2.1, 11.2.2, and 11.3.
BSIDv03 Gross and Fine Motor Subtests (with video)	X							X		X		X		X		X	See Sections 11.1, 11.2.1, 11.2.2 and 11.3.
CHOP INTEND (with video)	X	X				X	X	X	X		X		X		X	X	See Sections 11.2.3 and 11.3. Patients who achieve 3 consecutive CHOP-INTEND scores ≥ 58 will not continue CHOP-INTEND assessments.
Demographic/Medical History	X																See Section 12.1.1.
Physical Exam	X		X	X	X	X	X	X	X		X		X		X	X	See Section 12.1.2
Vital Signs/Weight & Length	X	X	(X)	X	X	X	X	X	X		X		X		X	X	See Section 12.1.3. (X): Vital signs will be continuously monitored throughout the infusion of gene replacement therapy and recorded every 15 minutes (+/- 5 minutes) post dose for the first 4 hours after the start of infusion, then every hour (+/- 15 minutes) until 24 hours after the start of infusion. Axillary

Trial Period	Screen-ing	Gene Replacement Therapy (In-patient)					Follow-up (Outpatient)										Notes	
		-30 to -2	-1	1	2	3	7	14	21	30	44	60 (or Month 2)	72	90 (or Month 3)	Month 4,5,7,8,10,11,13	Month 6,9,12	End of Trial (18 months of age or ET)	
Nominal Study Day (Visit Relative To Dose)																		Depending on the patient's age at dosing, the duration of participation can vary from approximately 12 months (baby dosed at approximately 6 months of age) to approximately 18 months (baby dosed near birth, "0 months of age").
Visit According To Months of Age															14,16,17	15		
Window	(No Window)					± 2 days				± 7 days (Except +0–14 days at 14 Months of Age)				+0–14 days				
																	temperature will be recorded pre- and post-infusion.	
12-Lead ECG	X			X					X					(X)	(X)	(X)	X	See Sections 12.1.4, 12.1.5, and 12.1.6 .

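### The treatment-emergent rule cuts at calendar Day 1 rather than at infusion start, so an adverse event arising on Day 1 before the vector is given would count as treatment-emergent (minor)

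*SAP*

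**What the plan says.** SAP 2.1.1 states that Day 1 "is defined as the day of gene transfer" and that a treatment-emergent adverse event (TEAE) "is any AE whose onset or worsening occurred on or post Day 1". Neither definition mentions a clock time. In the same section, baseline "refers to a non-missing measurement or evaluation made prior to initiation of gene therapy infusion", so the baseline rule does cut at the infusion.

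The protocol places procedures on Day 1 before the vector is given. Section 12.1.2 says: "The Day 1 physical examination will be performed prior to the start of gene replacement therapy infusion". The schedule in Appendix 1 says the same of the Day 1 visit: "Day 1 assessments will be performed prior to the start of gene replacement therapy infusion". Section 12.1.2 also says: "Any clinically significant abnormal finding should be recorded as an adverse event".

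Adverse events are collected from consent (protocol 13.1.1). For each one, under protocol 13.3, "the Investigator will evaluate and report the onset (date and time [if start date during inpatient period"; the inpatient period runs from Day -1 to Day 3 (protocol 7.1). The protocol's abbreviation list gives Day 1 a different meaning: "First 24-hour interval after the start of gene replacement therapy infusion".

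SAP 2.7 and 2.7.1 keep an adverse event overview and tabulate TEAEs and serious TEAEs by system organ class and preferred term. SAP 4 confirms that these three tables are the only exception to listings and patient profiles.

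**The concern.** A TEAE rule is meant to separate what arose after treatment began from what was there before. As written, it puts the hours from midnight to infusion on Day 1 on the treated side. A new, clinically significant finding at the pre-infusion Day 1 examination could then be the baseline value in the examination listing (SAP 2.7.4.3) and a TEAE in the adverse event table. The overview has separate lines for any adverse event and any TEAE, and the difference between those lines depends on this cut. What is at stake is the accuracy of a few descriptive tables, not an inference. The onset time needed for a correct split is already being recorded.

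**Working it through.** The plan gives no figure on this point, so there is none to reproduce. The check applies two rules to the same onsets.

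**Inputs.** The date rule comes from SAP 2.1.1: onset date on or after Day 1. The alternative is onset date and time at or after infusion start. There are 2 enrolled patients (SAP 1.1, protocol 7.2). The documents give no clock times, so an examination at 08:00 and an infusion start at 11:00 are assumed for illustration.

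| Onset | SAP date rule | Infusion-start rule |
|---|---|---|
| Day -1, 20:00 | not a TEAE | not a TEAE |
| Day 1, 08:00 (before infusion) | **TEAE** | **not a TEAE** |
| Day 1, 13:00 (after infusion) | TEAE | TEAE |
| Day 2, 09:00 | TEAE | TEAE |

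Only the pre-infusion part of Day 1 is classified differently. If infusion starts between 08:00 and 14:00 (assumption), that window is 8 to 14 hours.

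**Conditions for an event to be affected.** It must be recorded as an adverse event, and its onset or worsening must be dated Day 1 before infusion. A pre-existing finding dated earlier and unchanged is not affected. The schedule, as it reads in the available text, shows a physical examination at screening and on Day 1 but none on Day -1, so a finding first seen on Day 1 could plausibly be dated Day 1.

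**Effect on a row.** SAP 2.7.1 counts a patient once per preferred term, once per system organ class and once overall. If the affected infant has no post-infusion TEAE counted on that row, the patient count rises by 1 of 2 = 50 percentage points. If the infant has one, the patient count and percentage stay the same, and only the number of events can rise. Any single event in a two-patient trial moves a row by 50 points, so this figure reflects the denominator and does not measure the rule.

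**Chance that either infant is affected.** If each infant has probability p of such an event, independently, the chance that at least one of 2 is affected is 1 - (1 - p)². The documents give no p. Over an assumed range:
- p = 0.05: 1 - 0.95² = 9.75%
- p = 0.10: 1 - 0.90² = 19%
- p = 0.20: 1 - 0.80² = 36%
- p = 0.30: 1 - 0.70² = 51%

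**Related rule.** SAP 5.1.2 moves an event known to precede treatment to the treatment date when imputation would put it later, and moves an on-treatment event to the treatment date plus one day. That rule uses the treatment date as the pre-treatment side, while the TEAE rule uses the same date as the treated side.

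**The case against.** The strongest reply is that a day-level cut is over-inclusive: it can add an event to a safety table but cannot hide one. With 2 infants, every event can also be checked in the listings and profiles. Investigators judge causality for each event (protocol 13.2), so an event before the vector should be called unrelated and stay out of the related-event lines. All of this stands, and it is why the point is minor. It is not a reason to keep the rule, because onset times are collected and the fix keeps the inclusive default where a time is missing.

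One can also argue that prednisolone and the venous catheter are part of giving this treatment, so events from them may fairly count as emergent. But prednisolone starts on Day -1 (protocol 9.2.1), so a cut at midnight on Day 1 captures neither the whole regimen nor the vector alone. The documents do not say when the catheter is placed, so nothing here rests on line placement.

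A reader might infer several stronger things that the documents do not support:
- **That findings from the pre-infusion examination are all tabulated as TEAEs.** The rule turns on the date of onset or worsening, not of detection.
- **That the protocol and SAP classify the same event differently.** The protocol has no TEAE definition. Its own use of Day 1 is also mixed: the abbreviation list starts Day 1 at the infusion, sections 12.1.2 and 12.1.3 and Appendix 1 place Day 1 procedures before it, and section 14.4.1 sets baseline at day level.
- **That TEAEs are all that is aggregated.** The overview also has lines for any adverse event and any serious adverse event, which are the same under either cut.

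**Conclusion.** The point holds as a minor inconsistency. By its wording, the SAP counts an adverse event with onset or worsening on Day 1 before infusion as treatment-emergent, while its baseline rule treats that time as pre-treatment. The error can only add events. It is confined to the TEAE and serious TEAE tables and the TEAE lines of the overview, in 2 infants, and related-event lines should be little affected. A patient count changes by 1 of 2 only when that infant has no post-infusion TEAE on the same row. No hypothesis test or comparison is involved. The conclusion rests on reading the SAP's Day 1 as a calendar day, which is its natural sense. Whether any such event occurred cannot be told from the documents.

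**What to change.** In SAP 2.1.1:
- Define a TEAE as an adverse event with onset or worsening at or after the date and time the infusion started.
- Keep Day 1 events with a missing onset time as treatment-emergent, except those known to precede treatment whose start date was set to the treatment date under SAP 5.1.2.
- List Day 1 pre-infusion events as pre-treatment.
- State which definition of Day 1 governs, the SAP's day of gene transfer or the protocol's 24 hours from infusion start.

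The cost is a sentence or two of SAP text and one programming condition with its exception. No new data are needed, because protocol 13.3 already collects onset times for the inpatient period.
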